1 STUDY SUMMARY

1.1 Synopsis

Title:	Open label comparison of injectable extended release buprenorphine (CAM2038, Brixadi®) and naltrexone (Vivitrol®) for the treatment of opioid use disorder
Short Title:	Brixadi and Vivitrol
Study Description:	
This study will elucidate the cognitive mechanisms of response to opioid agonists and antagonists used to prevent relapse in OUD through investigation of the underlying neural circuits. We shall use previously validated cognitive probes, functional Magnetic Resonance Imaging (fMRI), and extended-release injectable preparations of opioid partial agonist buprenorphine (XR-BUP, Brixadi) and opioid antagonist naltrexone (XR-NTX, Vivitrol), in OUD patients. Using two medications with opposing mu opioid receptor action will allow a comprehensive evaluation of the mechanisms of response to relapse prevention pharmacotherapy in OUD. The study will determine the presence of treatment effects in the domains of executive function, incentive salience, and resting functional connectivity and the interaction that will indicate a difference between the two medications. Then we will evaluate the ability of the brain fMRI signal to explain relapse defined by % of opioid-positive urine tests and adherence to the study interventions. Participants will be recently detoxified treatment-seeking patients with OUD who will receive 3 monthly injections of XR-NTX or XR-BUP and have weekly urine toxicology monitoring. The project will enroll 200 participants over 6 years. The proposal would be the first neural systems' level investigation of the cognitive effects of the next generation extended release preparation of buprenorphine and naltrexone to explain the individual heterogeneity of OUD treatment response and failure. This project has the potential to advance the theory and personalized treatment of OUD by elucidating the brain mechanisms of vulnerability to relapse in OUD and in SUD in general.
 
The proposal is similar to an existing UPenn IRB protocol 814234 and Biomarkers of disease and response to treatment in opioid addiction in all aspects except the addition of XR-BUP, Brixadi.

Objectives:	Compare brain fMRI response to injectable extended-release buprenorphine (Brixadi, XR-BUP) and naltrexone (XR-NTX, Vivitrol)

**Medications
and
Interventions**

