3.1 General Design

Study Design: The proposed study is a prospective open label 2-group study to compare the brain and behavioral responses of individuals with OUD receiving XRBUP and XRNTX treatments. The study will be conducted in two phases – Phase 1 = feasibility and Phase 2 = confirmation. Study interventions (XRNTX and XRBUP) and their duration will be same in both phases. Phase 1 (2 years) will have more cognitive and behavioral probes, some of which may not survive into Phase 2 (3 years) if found to not yield significant discrimination between the study interventions (groups). Participants will be men and women with current DSM-5 diagnoses of opioid use disorder (OUD) who will be randomized to XRBUP or XRNTX. Phase 1 will recruit 60 participants and Phase 2 will recruit 200 participants. The study length for each participant is comprised of up to 30 days of screening and baseline evaluations (called “week 1”), a 12-week open label trial (medication phase), and one follow-up visit 4 weeks after end of medication phase. The overall duration of the project will be 5 years (60 months). We intend to recruit 4 subjects per month for 40 months.

Table 1. Study timeline

Year/Phase	Year 1 (Phase 1)				Year 2 (Phase 1)				Year 3 (Phase 2)				Year 4 (Phase 2)				Year 5 (Phase 2)			
Quarter	Q1	Q2	Q3	Q4																
Preparation	X	X	X	X					X	X										
Recruitment		X	X	X	X	X	X	X	X	X	X	X	X	X	X	X	X			
Data Collection		X	X	X	X	X	X	X	X	X	X	X	X	X	X	X	X			
Data Analysis/QC			X	X	X	X	X	X	X	X	X	X	X	X	X	X	X	X	X	X
Publication				X	X			X	X			X	X			X	X	X	X	X

Figure 1: Outline of study interventions

3.2 Primary Study Endpoints (see Table in the Schedule of Activities (SoA), [Appendix Section 12.1](#)).

Clinical:

- 1) percent of the urine drug screen (UDS) tests positive for opioids during the last month of participation.
- 2) The number of study interventions (1,2 or 3) participant adhered to.

Surrogate: Brain fMRI response in three cognitive domains:

- 1) Response inhibition (Go-NoGo task)
- 2) Drug cue reactivity (Opioid Cues task)
- 3) Emotional identification (IDemo Task)
- 4)

Primary Hypothesis:

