Biochemical Assessments:

Urine Toxicology: Rapid semi-quantitative ELISA urine drug screen test for morphine, oxycontin, methadone, buprenorphine, fentanyl, cocaine, amphetamine, methamphetamine, benzodiazepines, PCP and THC. Urine sample collection procedure has been described in a recent paper (Wang et al 2015).

Neuroimaging and cognitive: Overview of BOLD fMRI paradigms design: BOLD fMRI is a relative (non-absolute) measure, and experimental results are typically reported as contrast between conditions. Two main strategies are event-related and block designs (Aguirre et al 1999, Laurienti et al 2003).

Resting-state fMRI (rs-fMRI): During the 5-min rs-fMRI, participants will be instructed to stay awake, still, and to keep their eyes open. A fixation crosshair will be shown on a black background throughout the scan. No task performance will be required.

Visual Opioid Cue Task: Forty-eight drug-related and 48 control stimuli are presented randomly for 500 msec, separated by variable inter-trial intervals (ITI, 0–18 s). The stimuli sets are tailored to a specific pattern of OUD: prescription opioids only, heroin (IV and IN) only, and mixed prescription opioids and heroin (Shi 2016). The control stimuli that depict household objects and

chores are graphically and contextually matched to the drug-related stimuli (Langleben et al 2008, Wang et al 2015). Opiate craving is assessed with a subjective craving score (SCS), before and after each MRI session on a 0–9 Likert scale. There is no response requirement in the task, avoiding the possible confounds of individual differences in motor coordination/reaction time.

fMRI Go-NoGo task (GNG): The Go-NoGo fMRI task is a validated task testing cognitive control aspect of executive functions adopted from previous research (Goldman et al 2015). The Go stimuli included 122 positively valanced pictures (e.g. sweets), and the No-go stimuli were 38 negatively valanced pictures (e.g. snakes). Each trial consisted of a stimulus displayed for 300 ms, followed by 1700-ms baseline period during which a crosshair was displayed. Pseudo-random order of the stimuli and baseline periods was generated. Total Task Time: ~8 min. Our preliminary task performance data indicate that Go-NoGo task performance predicted XRNTX treatment failure ($p<0.01$). Performance will be coded by the number of errors of commission.

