Hamilton Depression Rating Scale (HAM-D) (Hamilton 1959). The HAM-D is a 20-minute, 24-item interview that measures the severity of depression and changes in depressive symptoms.

Clinical Opiate Withdrawal Scale (COWS) (Wesson et al 2003). The COWS is a clinician-administered instrument that measures eleven common opioid withdrawal symptoms.

Short Form-McGill Pain Questionnaire-2 (SF-MPQ-2) (Dworkin et al 2015) (PhenX #190901) is a 22-item self-administered questionnaire that asks about the different qualities of pain and related symptoms. Respondents are asked to rate the intensity of each type of pain they felt during the past week on a scale from 0 to 10

Timeline Follow-Back Interview (TLFB) (Sobell et al 1992). The TLFB is a 15-30-minute, semi-structured interview designed to measure self-reported drug use. It will be used at baseline to capture all drug use in the past 30 days including prescribed concomitant medications (PhenX 27016266).

Weekly online self-reported TLFB is a modified TLFB interview that uses a calendar-based format to record participants' self-report of past week drug use.

Experimental Assessments:

Urine Toxicology: Rapid semi-quantitative ELISA urine drug screen test for morphine, oxycontin, methadone, buprenorphine, fentanyl, cocaine, amphetamine, methamphetamine, benzodiazepines, PCP and THC. (Urine sample collection procedure has been described in a recent paper (Wang et al 2015).

Neuroimaging and cognitive: Overview of BOLD fMRI paradigms design: BOLD fMRI is a relative (non-absolute) measure, and experimental results are typically reported as contrast between conditions. Two main strategies are event-related and block designs (Aguirre et al 1999, Laurienti et al 2003).

Resting-state fMRI (rs-fMRI): During the 5-min rs-fMRI, participants will be instructed to stay awake, still, and to keep their eyes open. A fixation crosshair will be shown on a black background throughout the scan. No task performance will be required.

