9 STATISTICAL CONSIDERATIONS

9.1 Statistical Hypotheses

Overview of primary hypotheses: Our primary response will be a binary indicator of treatment failure on the XRNTX or XRBUP regimen, defined as ≥ 2 weekly UDS positive for opioids, or self-report of ≥ 2 periods of three or more days of opioid use, or refusing XRNTX or XRBUP, or dropping out of study entirely. In hypotheses H1a and H1b, we are examining the effects of small, pre-specified, sets of measures, so our analyses will focus on model fit and prediction, and not on model selection. In hypothesis H1c, we search for best sets of predictors among demographic and clinical-behavioral variables, and over sets of brain/neural measures, so our focus is on model selection and on avoiding overfitting to the available data.

R61 Phase:

Hypothesis H1 (fMRI): For each of the cue reactivity (H1a), response inhibition (H1b), and connectivity (H1c) brain measured, we have a small number of neural responses associated with one or two regions of interest. These variables are continuously distributed, so we will test Hypotheses 1a, 1b and 1c using a repeated measures analysis of variance (rm-anova). The models will include a within-subject factor for Session (PRE vs ON) and a between-subject factor Group (XRNTX vs XRBUP), and their interaction. To accommodate the anticipated non-normal distributions of the response, we will use a generalized estimating equation (GEE) approach, using robust standard errors, using a compound symmetry working correlation structure for the within-subject correlations between the PRE and ON fMRI scans (Diggle PJ et al 2002). We will perform the rm-anova separately for each ROI (mPFC and VS for H1a, IFC for H1b, and VS-rtIFG and VS-mPFC for H1c). The hypotheses will be addressed by the Session by Group interaction, and we will obtain estimates and standard errors of the PRE vs ON change within each of the two groups, along with the size, standard error and significance of the differences between these estimates.

Sample size considerations for sample: The sample size is adequate for application of the GEE methods to obtain robust standard error (Lipsitz et al 1994). For a test of the PRE vs ON effect, our sample yields 80% power for a one-sided test that the ON levels will be Cohen's $d=0.4$ lower than the PRE levels, consistent with a decrease of Cohen's $d=0.5$ observed in our preliminary data and a decrease of Cohen's $d=0.3$ in the Suboxone sample.

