Effects of neural response on relapse vulnerability: Our primary outcome combines adherence to treatment and frequency of illicit opioid use during treatment. The primary outcome is a binary indicator of treatment success: if a patient provides ≥ 2 weekly UDS positive for opioids, or self-report of \geq two or more periods of ≥ 3 days of opioid use, or refuses XRNTX or XRBUP, or drops out of treatment entirely, then they will be classified as a treatment failure; otherwise they will be classified as a treatment success. We will calculate the PRE-ON change in %-signal-change for each of the regions and neural responses described in the R61 phase. We will use logistic regression models to predict the log-odds of treatment success (Aitkin et al 2009). The predictors in the model will be a binary factor for Group (XRNTX vs. XRBUP), and the neural change scores. We anticipate that there will be some greater PRE to ON changes in the XRNTX group than in the XRBUP group, so there will be some confounding between the effects of change score and the effects of Group on the rates of positive UDS. Thus, we will include Group first in our model, so evaluating the Group effect separate from the change-score effects, and then include the change scores in a model including Group, so evaluating the additional effect of change-scores in addition to the existing effects of Group. To assess whether the effects of the change scores differ between the XRNTX and XRBUP groups, we will also test for interaction effects between Group and each of the change-scores, by adding the interaction terms to the model that includes the group and neural change score main effects. We will check the assumptions underlying the logistic regression models (e.g. linearity of covariates effects on log-odds, outliers, influential observations) using standardized residuals, influence diagnostics, and graphical displays.

Sample size considerations for the sample: Analyses of Session by Group effects on neural response: For a one-sided test that the PRE vs ON effect is larger in the XRNTX group than in the XRBUP group, our sample of 70 per group yields 81% power for an effect of $d=0.42$ or greater. This effect is similar to the effects observed in the preliminary data. On the basis of the preliminary data we anticipate Group by Session effects of approximately $d=0.38$ in the VS and $d=0.42$ in the mOFC.

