Missing Data and Nonadherence: For the longitudinal analyses described above, premature discontinuation from treatment and occasional missing daily use indicators will lead to incomplete data. The mixed effects models described above can make use of all available data provided by subjects, but the inferences drawn from them will be unaffected by the missing data only if the missing data can be regarded as ignorable, in the sense of Laird ⁵⁵. To assess the sensitivity of our analyses to this assumption, we will use shared parameter models, which allow for correlated random effects underlying the cocaine use measurements and the pattern of dropout ⁵⁶. We will also use selection models to examine the effects of missing data ^{57,58}. We will explicitly model the probability of premature discontinuation at a time point as a function of baseline characteristics and responses at previous time points, using a logistic regression model, and incorporate the predicted probabilities into a weighted analysis of the main hypotheses. We will do analyses in a range of assumptions and assess the sensitivity of results to them ⁵⁸. We will use urine drug screens, record of clinic visits and receipt of injectable medications as measures of compliance with assigned medication regime. We will use the methods of Nagelkerke et al ⁵⁹ and Small et al ⁶⁰, to obtain estimates of the intervention effect in a population compliant with treatment i.e. the Complier Average Causal Effect (CACE).

Safety: The adverse event responses will be analyzed as a measure of safety. Total number of adverse events, adverse events leading to discontinuation (in the judgment of the study physician), % of patients reporting at least one adverse event, clinical lab assessments, vital signs and

evidence of clinical worsening (by urine drug screen results and TLFB results) will be considered in assessment of safety. In a manner parallel to the analysis for therapeutic response, medication group, gender, age and other clinical variables will be entered into a generalized linear mixed effects model to predict adverse events.

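### The urine outcome does not say which opioids count, and the panel detects buprenorphine; scored as written, nearly all XRBUP participants would be treatment failures

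*Combined protocol and SAP*

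**What the plan says.** Section 6.1 (Biochemical Assessments) describes the urine test as a "Rapid semi-quantitative ELISA urine drug screen test for morphine, oxycontin, methadone, buprenorphine, fentanyl, cocaine" and further non-opioid drugs. Section 8 repeats the list. The Synopsis describes XRBUP as buprenorphine, a partial opioid agonist, and provides for weekly urine testing. Section 6.1 also allows supplemental sublingual buprenorphine/naloxone during XRBUP induction.

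The outcomes that use this test are:

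- Section 3.2, first clinical primary endpoint: "percent of the urine drug screen (UDS) tests positive for opioids during the last month of participation".
- Section 9.1, overview: a "binary indicator of treatment failure on the XRNTX or XRBUP regimen, defined as ≥ 2 weekly UDS positive for opioids", or on self-reported use, refusal of injections or dropout.
- Section 9.1, Phase 2: "Our primary outcome combines adherence to treatment and frequency of illicit opioid use during treatment". The operational rule that follows again counts "≥ 2 weekly UDS positive for opioids", without the qualifier illicit.
- Section 9.4.1, Safety: clinical worsening is judged partly from urine screens.

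No section lists the analytes that make a screen opioid-positive, and none says how a buprenorphine-positive result is scored in either arm.

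**The concern.** Buprenorphine is an opioid by the protocol's own description, it is on the panel, and one arm receives it as a depot. A data manager who follows the rule has no stated basis for ignoring a buprenorphine-positive screen. The document's own usage points the same way: the washout requirement for XRNTX in section 2.3.1 treats buprenorphine as a form of opioid use, with its own interval.

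If those results count, the outcome in the XRBUP arm records exposure to the assigned drug and not relapse. That would affect the percent-positive endpoint, the failure outcome, the Group term and Group-by-change-score interactions in H2a, the H2b models, and the weekly opioid measure among the polysubstance outcomes.

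The stated aim rules out counting study drug but does not settle the scoring. Buprenorphine could be dropped in XRBUP only or in both arms. Dropping it in XRBUP only is asymmetric: a buprenorphine-positive urine would be relapse on XRNTX and never on XRBUP. In an open-label trial this choice should not be left until data have been seen.

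**Working it through.** **Inputs from the documents.** Weekly urine tests (Synopsis); a 12-week medication phase (section 3.1), so about 12 tests; failure at two or more positives (section 9.1); 140 participants, 70 per group (section 9.1); assumed Group odds ratio 1.25, with 80% power for an odds ratio of 1.75 per SD of a neural variable at alpha 0.05 and 1.86 at alpha 0.025 (section 9.1).

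**Inputs that are assumptions.** The per-test probability *s* that the assay detects depot buprenorphine, independence of tests within a person, and the outcome rate *p*. The documents give none of these.

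**Step 1: the plan's own power figure.** For one continuous predictor in logistic regression, n = (z_alpha + z_beta)² / [p(1-p) (ln OR)²]. With n = 140, two-sided alpha 0.05 and 80% power:

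- p(1-p) = (1.960 + 0.842)² / (140 × 0.560²) = 0.179, so p = 0.234.
- The alpha 0.025, OR 1.86 figure gives p = 0.229.

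The two statements agree with each other if the less common outcome has a rate of about 0.23. They cannot be reproduced from the documents alone, because p is not given.

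**Step 2: chance that an XRBUP participant meets the urine limb through study drug.** P(two or more of k) = 1 - (1-s)^k - k s (1-s)^(k-1). For k = 12 and s = 0.3 this is 1 - 0.0138 - 0.0712 = 0.915.

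| Assumed detection *s* | 12 tests | 8 tests |
|---|---|---|
| 0.3 | 91.5% | 74.5% |
| 0.5 | 99.7% | 96.5% |
| 0.7 | >99.9% | 99.9% |
| 0.9 | about 100% | about 100% |

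A participant with few samples because of dropout or refused injections already fails under the same rule.

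**Step 3: XRBUP successes left among 70, with 12 tests.** At s = 0.3, at most 70 × 0.085 = 6 on average; at s = 0.5, 70 × 0.0032 = 0.2. Genuine failures reduce these further.

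**Step 4: size of the artefact.** Artefact = 100% minus the true XRBUP failure rate, taking the recorded rate as about 100%. For an assumed true rate of 25-50% this is 100 - 50 = 50 to 100 - 25 = 75 points.

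**Step 5: effect on the logistic models, in the limit of no XRBUP successes.** Group is then separated from the outcome: there is no finite odds ratio to set against the assumed 1.25, and Group-by-change-score interactions cannot be estimated. Only the 70 XRNTX participants inform the neural effect. Power for OR 1.75 at two-sided alpha 0.05 is Φ(√(70 p(1-p)) × 0.560 - 1.960):

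- p = 0.20: Φ(1.873 - 1.960) = 47%.
- p = 0.50: Φ(2.341 - 1.960) = 65%.

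A simulation with likelihood-ratio tests (2,000 runs per setting, XRNTX success rates of 0.25 to 0.75) gave 49-60%. The odds ratio detectable with 80% power rises to about 1.95-2.31.

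**The case against.** The strongest reply is that the plan plainly does not mean to count study drug. Its outcome paragraph opens with illicit use, section 9.4.1 lists urine screens among its compliance measures, and a Group odds ratio of 1.25 could not coexist with near-total failure in one arm. This is persuasive about intent, and it makes a missing scoring rule more likely than a planned misclassification. It does not supply the rule: the qualifier is absent from the operational definition and from section 3.2.

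Several stronger readings are tempting and not supported:

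- A reader might infer that every XRBUP participant fails, at exactly 100%. The documents give neither a cutoff nor a detection rate. Results within a person would also be correlated, so the percentages above are indicative, most of all at low detection.
- A reader might take the 50-75% XRNTX retention cited in section 4.1 and call the resulting 50-75 point gap between arms artefact. The artefact is measured against the true XRBUP rate, not the XRNTX rate, and retention misses the other limbs of the failure rule.
- A reader might conclude that the whole trial is compromised. The Synopsis makes the fMRI Group-by-Session interaction the primary endpoint and urine toxicology secondary. H1a-c do not use urine results, and H2b is labelled exploratory. Sections 3.2 and 9.1 nevertheless call the urine-based outcomes primary, so they matter.
- The self-report and safety limbs are weaker. A staff-given injection is not naturally reported as a period of opioid use, and clinical worsening need not follow from one positive analyte.

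It is also fair to say that excluding buprenorphine in both arms is one defensible choice and not the only one. On XRNTX, non-study buprenorphine can be illicit opioid use, which is the stated target.

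**Conclusion.** The concern holds as an incomplete endpoint definition that gives a wrong result if followed literally. Provided the assay detects depot buprenorphine, nearly all XRBUP participants would be classed as failures: 91.5% by the urine limb alone at an assumed detection of 0.3 and 99.7% at 0.5, over 12 tests treated as independent. The artefact is 100% minus the true XRBUP failure rate, which the documents do not give; 50-75 points is an illustration for a true rate of 25-50%.

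With almost no XRBUP successes, the Group odds ratio and the H2a interactions could not be estimated, and the H2b models and the weekly urine opioid measure would carry the same artefact. The fMRI Session-by-Group tests stand. The definition should be settled before any outcome is scored.

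**What to change.** In sections 3.2 and 9.1, define an opioid-positive screen by named analytes so that study-supplied buprenorphine, including any sublingual supplement, never counts as use.

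- **Main between-arm analysis:** use one analyte set in both arms: morphine, oxycodone (taken to be what the panel lists as oxycontin), methadone and fentanyl.
- **Sensitivity analysis, prespecified:** count buprenorphine-positive urine as use in XRNTX.
- **Self-report limb:** define opioid use as non-study, non-prescribed use.
- **Buprenorphine results in XRBUP:** report them only as an exposure check.
- **Safety:** apply the same definition wherever urine results inform clinical worsening in section 9.4.1.
- **Panel:** reconcile the ten-drug screen in the Schedule of Activities (13.1) with the eleven analytes listed in section 6.1.

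The cost is a few sentences. No new data should be needed if results are stored by analyte, which the planned cocaine endpoint (section 3.3) and substance-specific measures (section 9.1) suggest. The downside is that non-study buprenorphine use on XRNTX is counted only in the sensitivity analysis. On XRBUP it cannot be told apart from study drug by this urine screen under any scoring rule.

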Predictive modeling: The models for relapse/treatment-success addressed the effects of neural responses, in isolation from demographic and clinical measures. In further analyses, we will examine their effects in combination with demographic and non-imaging clinical predictors. As we can expect overlap between the effects of these sets of variables, we compare the effects of these domains on prediction of treatment success. Thus, we will compare models using various sets of predictors on the basis of AUC comparisons, rather than on goodness of fit (Sullivan Pepe 2003). In our model search, we will compare models containing interactions between Group and the various predictors, with the constraint that an interaction is included only in models where the corresponding main effects are also included. First, we will find the best fitting demographic model, searching over a set including age, race, gender, and educational status. Next, with the predictors from the best demographic model included, we will search over the clinical predictors (depression and anxiety scores, measures of withdrawal and craving, and the ASI composite scores) to find the set that most improves the predictive utility of the best demographic model. Third, with the predictors from the best demographic/clinical model included, we will search over the measures of neural change to find the set that most improves the fit of the best demographic/clinical model. We will then perform goodness of fit and ROC comparisons between the best demographic, demographic/clinical, and demographic/clinical/brain models. This process involves three searches over various sets of variables, and unconstrained searches are likely to yield complex models involving many predictors, resulting in a prediction rule that performs poorly in new samples. To avoid this, we will use a lasso approach to fitting the logistic regression models for this hypothesis. The usual algorithms for logistic regression estimate the model parameters by minimizing a measure of lack of fit of the model to the data, but do not penalize models for complexity. The lasso approach selects a best fitting model subject to the constraint that the sum of the magnitudes of the regression coefficients in the model is less than a small positive threshold value. The threshold is chosen adaptively from the data, by minimizing an estimate of the prediction error for the model, using ten-fold cross validation. Then, a best fitting model is chosen with the estimated threshold used in the penalty. The best fitting model is usually one in which a number of the coefficients are set to zero, i.e. a number of predictors are dropped from the model.

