13 APPENDIX

13.1 Schedule of Activities (SoA)

	Screening detox and randomization (Day -14)	MRI Scan 1 Baseline (day 0)	Induction to XRBUP or XRNTX (day 0-10)	Injection 1 (day 10) + weekly follow up	Injection 2 (day 40)	MRI Scan 2 On Treatment (day 55)	Injection 3 (Day 70)	Weekly Follow- up End of study and referral (Day 100)
Psychiatric and medical								
Demographics (age ¹ , sex ¹ , edu ¹)		X						
History, physical and labs (C.4.a)		X						
SILS		X						
MINI (EOS* – end of study)		X						X EOS*
Addiction Severity Index ¹		X						X EOS*
Clinical/Behavioral (C.3.a)								
HAM-D ² , HAM-A ² , COWS ²	X	X	X		X	X		X
SOWS, Opioid Craving Scale ² , SF-MPQ-2 ² , STAI-6		X	X	X	X	X		X
TLFB interview	X	X	X		X	X		X
Ten-drug urine drug screen (UDS)	X	X	X	X	X	X		X
Go-NoGo errors of commission ²		X		X				
Neuroimaging (Section C.3.b)								
Go-NoGo fMRI ³		X			X			
Opioid Cue task fMRI ³		X			X			
Resting-state fMRI ³		X			X			
MPRAGE (anatomical MRI scan)		X			X			

PRINCIPAL INVESTIGATOR SIGNATURE

STUDY SPONSOR: [name]

STUDY TITLE: **Open label comparison of injectable extended release preparations of buprenorphine (Brixadi®) and naltrexone (Vivitrol®) for the treatment of opioid use disorder**

STUDY ID 843403

PROTOCOL VERSION V5.0

I have read the referenced protocol. I agree to conduct the study in accordance to this protocol, in compliance with the Declaration of Helsinki, Good Clinical Practices (GCP), and all applicable regulatory requirements and guidelines.

Principal Investigator Name	[name]	Signature
Affiliation:	University of Pennsylvania	Date 7/17/2023

END OF DOCUMENT

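### H2a and H2b relate failure at any time on treatment to a change score that needs the day-55 scan, so they cannot show that brain change precedes relapse

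*Combined protocol and SAP*

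**What the plan says.** Under the relapse-vulnerability heading of Section 9.1, the outcome is described so: "Our primary outcome combines adherence to treatment and frequency of illicit opioid use during treatment". A participant fails with two or more opioid-positive weekly urines, with two or more self-reported use periods of at least three days, by refusing the injection, or if he or she "drops out of treatment entirely, then they will be classified as a treatment failure". No start or end date is given. The overview at the head of Section 9.1 counts leaving the study; this later text counts leaving treatment.

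The H2a predictors are Group and the neural change scores: "We will calculate the PRE-ON change in %-signal-change for each of the regions and neural responses described in the R61 phase". H2b (Predictive modeling, Section 9.1) uses the same scores: "we will search over the measures of neural change to find the set that most improves the fit".

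The Schedule of Activities (Section 13.1) has injections on days 10, 40 and 70, a column headed "MRI Scan 2 On Treatment (day 55", and a final column that reads "End of study and referral (Day 100".

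Other time frames appear elsewhere. Section 3.1 gives "a 12-week open label trial (medication phase", Section 4.1 argues from 70 days, and Section 4.2 refers to outcomes at two months. Section 3.2 lists a separate clinical endpoint, "percent of the urine drug screen (UDS) tests positive for opioids during the last month of participation", which the H2a composite does not use.

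**The concern.** The predictor is measured part-way through the period in which the outcome can occur. This has two consequences.

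1. **Time order.** A participant with two positive urines in the first month is already a failure when scanned. If that use affects the on-treatment signal, the association runs from outcome to predictor.
2. **Missing predictor.** Someone who leaves before the scan is a failure by definition, has no change score and drops out of the logistic model. No rule covers this case.

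What is at stake is interpretation. H2a asks whether brain signal explains treatment failure, and H2b asks whether brain measures improve a clinical prediction model. Readers will want to take a positive result as brain response foreshadowing relapse.

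**Working it through.** **1. Timeline.** With weekly urines counted from injection 1 on day 10, tests fall on days 17, 24, 31, 38, 45 and 52. That is six tests and two injections before day 55. After the scan there are two tests if the window ends at day 70, four if it is 12 weeks from day 0 (day 84), and six if it is 12 weeks from day 10 (day 94).

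**2. Do the missing-data methods help?** The pattern-mixture and selection models in Section 9.1 serve the weekly substance-use models, whose predictors include the same change score. Section 9.4.1 adds shared-parameter models and weighting by the probability of discontinuation. These address missing outcomes. Everyone who leaves the study before the scan is a failure without a score, so weighting cannot supply one without further assumptions. None of the methods sets time order.

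**3. The plan's own power figure.** Section 9.1 states 80% power at odds ratio 1.75 (alpha 0.05) and 1.86 (alpha 0.025). It gives no failure rate. Use power = Φ(√[n·p(1−p)(1−R²)]·ln OR − z), with n = 140 from Section 9.1 and R² = 0.42²/(0.42² + 4) = 0.042 from the stated group difference of d = 0.42. Take p = 0.25 as an assumption; it equals the plan's expected dropout.
- √(140 × 0.25 × 0.75 × 0.958) = 5.01
- OR 1.75: Φ(5.01 × 0.560 − 1.960) = 80.1%
- OR 1.86: Φ(5.01 × 0.621 − 2.241) = 80.8%

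The pair fits 140 participants, all with a change score, and about 25% failing.

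**4. Cost of losing early leavers.** Same formula, 25% failing overall (assumed), OR 1.75:

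| Leave before scan | In model | Failures in model | Power | Detectable OR (80% power) |
|---|---|---|---|---|
| 0% | 140 | 35 | 80% | 1.75 |
| 10% | 126 | 21 | 63% | 1.98 |
| 12.5% | 122 | 18 | 56% | 2.09 |
| 20% | 112 | 7 | 29% | 3.06 |

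With 40% or 50% failing overall and 10% leaving early, power is 83% or 86%.

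**5. Time order.** A simulation of a logistic model (Group plus one change score) with no true effect. Assumed: 25% fail before the scan, half of them unscanned, and 15% of the rest fail later. With 140 treated: 35 early failures, about 122 scanned, 105 scanned and not yet failed, about 16 later failures. With 160 treated: 140 scanned, 120 not yet failed, 18 later failures.

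| Shift of ON signal from earlier use | Rejection, 140 treated | Rejection, 160 treated | Landmark |
|---|---|---|---|
| 0.1 SD | 5% | 5–6% | 4–5% |
| 0.2 SD | 8% | 8% | 4–5% |
| 0.3 SD | 12% | 13% | 4–5% |
| 0.5 SD | 24% | 27% | 4–5% |

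Repeat runs differ by about a point, hence 12–14% and 24–28% as rounded ranges.

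**6. H2b.** The relevant quantity is the gain over a clinical model. Take the base AUC of 0.76 from the preliminary data in Section 4.1, and let w be the share of scanned failures that failed before the scan (0.36–0.64 over the failure splits tried). Assuming independence, AUC ≈ Φ(√[d² + (w·shift)²]/√2) with d = √2·Φ⁻¹(0.76) = 1.00. The spurious gain from one score is about 0.000, 0.001–0.002, 0.001–0.004 and 0.004–0.011 at the four shifts. Several scores together could add more; that was not computed.

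**7. Landmark power.** For OR 1.75 with 15% failing after the scan:
- n = 105: √(105 × 0.15 × 0.85) = 3.66; Φ(3.66 × 0.560 − 1.960) = 53%
- n = 120: √(120 × 0.15 × 0.85) = 3.91; Φ(3.91 × 0.560 − 1.960) = 59%

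Simulation gives 50% and 55%.

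**The case against.** - **The plan claims only explanation.** H2a speaks of explanatory value and Section 4.2 of association. That is fair, but Section 9.1 also describes the models as predicting treatment success, so the limit should be written down.
- **The inflation is hypothetical.** This stands as to size. The documents do not say how far earlier use moves the signal. Section 2.2.1 regards illicit use under these medications as more psychological than pharmacological in meaning, and at 0.1 SD there is essentially no inflation. The gap in time order needs no such assumption.
- **Early failures may be few among those scanned.** Section 4.4 offers follow-up visits to those who stop medication, so some will be scanned. Section 7.2 permits withdrawal when an injection is more than 14 days overdue, and day 40 + 14 = day 54, so others may not be. The XRNTX retention of 50–75% in Section 4.1 refers to the third injection, on day 70 and so after the scan. The pre-scan failure rate is therefore unknown in either direction.
- **The last-month urine endpoint follows the scan.** It does for completers, but H2a does not use it.

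A reader might infer more than the documents support: that omitting early leavers biases the odds ratio, or that the stated power has no basis. Bias arises only if brain response relates differently to early leaving than to later failure. As for power, n is given and only the failure rate is missing.

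**Conclusion.** The gap is certain on the text: the failure window is not tied to the scan, and there is no rule for participants without a change score. As written, neither a significant odds ratio in H2a nor an AUC gain in H2b can be read as brain change preceding or predicting relapse.

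Its size is conditional. Under the assumed failure pattern, false rejection in H2a runs from about 5% to 24–28% for shifts of 0.1 to 0.5 SD. A reader might infer that an H2b improvement would be largely spurious; the calculated gain of at most about 0.011 from one score does not support that. Losing early leavers mainly costs failures and power.

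Nor does this undermine the trial's main comparison. The point does not concern the Group-by-Session test, and Section 9.4.1 lists H2a as secondary, although Section 9.1 calls treatment failure the primary response. The matter should be fixed before analysis.

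**What to change.** 1. State one failure window for H2a and H2b, and reconcile Sections 3.1, 4.1, 4.2 and 13.1 with it. Reconcile leaving the study with leaving treatment.
2. Keep the planned models, including the interactions, and label them associations that do not establish time order.
3. Add a pre-specified, supportive landmark analysis at each participant's actual ON-scan date, in those scanned and not yet failed, counting only failure reached after the scan. Adjust for any single pre-scan positive urine or self-reported use period, state whether it counts towards the two-event rules, and report intervals. Make no claim that brain change precedes relapse without support from this analysis.
4. State a multiplicity rule for the five scores. Tested at 0.05 each with correlation 0.3 (assumed), they carry a family-wise error of about 21%. One option is the 0.025 that Section 9.1 already mentions, applied within the two-variable domains; this controls error within a domain only.
5. Apply the same landmark to H2b, or label H2b descriptive.
6. Report by group how many fail before scan 2 and how many have no ON scan.
7. State the failure rate behind 1.75 and 1.86, and give the detectable odds ratio for the number expected to be scanned.

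A model of all failures on the PRE-scan signal is optional; it includes early leavers but does not test treatment response.

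**Cost.** SAP text and one added analysis from data already planned. The landmark answers a narrower question. Power of 50–59% at odds ratio 1.75 assumes 15% fail later. With the two adjusters it is about 44–47% (n = 105) or 51–53% (n = 120), if each item has 15% prevalence and an odds ratio of 1 or 5 with later failure. At alpha 0.025 it falls to about 28–36% (n = 105). If the window ended at day 70, only two urines would follow the scan and the analysis could only be descriptive.
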